## Sample Size and Statistical Methods

- **Sample Size:** The study included data from 1,485 trials across 6 subjects, representing a unique dataset of rare clinical cases.
- **Primary Statistical Test:** Coefficients were estimated using Restricted Maximum Likelihood (REML). Statistical significance was assessed with a pre-specified threshold of  $p < 0.05$ .
- **Adjustment for Multiple Comparisons:** No corrections were applied, as the analysis was limited to a small set of predictors.

- **Validation:** All analysis code was reviewed externally to ensure appropriate statistical methods and reproducibility.

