(<https://doi.org/10.1038/s41598-019-45416-4>). However, it is not clear whether this model will generalize to more complex stimulation patterns. We hypothesize that the shape and number of percepts elicited by multi-electrode stimulation depends on the geometric arrangement of activated nerve fiber bundles in the retina. Our model predicts that subjects should see a single phosphene when two activated electrodes stimulate the same optic nerve fiber bundle, and two phosphenes when the two electrodes stimulate distinct nerve fiber bundle.

We further hypothesize that object recognition can be improved by a stimulation strategy that minimizes accidental stimulation of passing nerve fiber bundles in the retina. We will use our computational model to predict which electrodes should be activated to produce a desired percept, and test whether this optimized stimulation strategy can improve behavioral performance.

The purpose of this research is to further our understanding of the visual experience of Argus II users. Clinical experience with existing devices makes it clear that the provided artificial vision differs substantially from normal sight. In the research proposed here, we will combine human behavioral measurements and computational modeling to try to develop better stimulation protocols for retinal implants.

Procedures

Overview. Our experiments are designed to quantify the perceptual experiences of retinal prosthesis patients. We will produce visual percepts in patients either by directly stimulating electrodes (using FDA-approved pulse trains) or by asking them to view a computer or projector screen and using standard FDA-approved stimulation protocols (as is standard for their devices) to convert the computer or projector screen image into pulse trains on their electrodes. All stimulation protocols will be FDA-approved.

Our experiments will follow standard procedures for collecting behavioral data on retinal prosthesis patients. Testing will be carried out within the ophthalmology department of our participating sites, in the clinical testing suite of the ophthalmological surgeon who helped with recruiting the patient. Use of the suite will require the permission of the ophthalmological surgeon who aids with recruitment, and co-ordination with the administrative staff member responsible for managing the ophthalmology clinic.

Methods

Retinal prosthesis setup

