## Introduction

This study evaluates spatiotemporal interactions between electrode pairs in Argus II retinal prosthesis users to understand how stimulation delay and retinal distance influence visual perception. The primary aim is to investigate the number of phosphenes elicited by varying spatial offsets (dist\_ret) and temporal delays (abs\_delay) between electrode pairs. The analysis explores both the main effects of these variables and their interaction on phosphene perception. As a Basic Experimental Study Involving Humans (BESH), the focus is on understanding the mechanisms of prosthetic vision in controlled experimental settings rather than direct clinical outcomes.

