## Study Design

- **Goal:** To measure the influence of spatiotemporal parameters on phosphene perception.
- **Hypothesis:** The number of phosphenes (num\_phosphenes) elicited by paired-electrode stimulation varies as a function of stimulation delay (abs\_delay) and retinal distance (dist\_ret), with the interaction of these variables hypothesized to modulate the response.
- **Approach:** Participants underwent paired-electrode stimulation while varying spatial offsets and temporal delays. A total of 35 conditions were tested, including combinations of delays (0 ms to 50 ms) and distances (proximal to distal electrodes). Stimulation protocols used single pulses on pairs of electrodes to probe responses at different time scales. Each participant's responses were recorded and analyzed for the number of phosphenes elicited under each condition.

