## Analysis Framework

- A **linear mixed model (LMM)** was selected to account for the hierarchical structure of the data, with subject\_id modeled as a random factor to capture inter-subject variability. Fixed effects included abs\_delay, dist\_ret, and their interaction (abs\_delay:dist\_ret).
- This model allows for the evaluation of the main effects of stimulation delay and retinal distance, as well as their combined interaction, on phosphene perception.
- No formal power calculation was conducted due to the rarity of the clinical population; the study leveraged within-subject comparisons to maximize statistical power.

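### Do three uncorrected tests at p < 0.05, with no stated rule for when the hypothesis is supported, require a change to the SAP?

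*SAP*

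**What the plan says.** The SAP's Study Design section states a compound hypothesis. The number of phosphenes "elicited by paired-electrode stimulation varies as a function of stimulation delay" and retinal distance, "with the interaction of these variables hypothesized to modulate the response". Analysis Framework fits a linear mixed model with subject as a random factor and says that it evaluates "the main effects of stimulation delay and retinal distance, as well as their combined interaction".

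In Sample Size and Statistical Methods, the entry for the primary test reads "Coefficients were estimated using Restricted Maximum Likelihood (REML). Statistical significance was assessed with a pre-specified threshold of" 0.05. The next entry deals with multiplicity: "No corrections were applied, as the analysis was limited to a small set of predictors". Outcomes names a single primary outcome, the phosphene count, and no decision criterion.

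The Introduction sets the tone: "The analysis explores both the main effects of these variables and their interaction on phosphene perception". It describes the work as a basic experimental study of mechanism rather than of clinical outcomes.

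**The concern.** The entry for the primary test gives an estimation method and a threshold. It does not name a coefficient, a joint test or a pattern of results that would decide the hypothesis. That hypothesis can be read in at least four ways: any one term suffices, all three are needed, the interaction decides, or the count varies with the predictors jointly. Having few predictors limits how far the error rate can rise, but it does not choose among these readings.

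The status of the tests also looks mixed. The Introduction speaks of exploring, while the later section uses the language of a primary test and a threshold fixed in advance. The protocol does not settle the matter. Its hypothesis under Purpose is that "the shape and number of percepts elicited by multi-electrode stimulation depends on the geometric arrangement of activated nerve fiber bundles in the retina", and it mentions neither stimulation delay nor a significance level.

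At stake is the sentence that says whether the hypothesis was supported, and the error rate behind that sentence. One set of results could be described either way.

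**Working it through.** **Inputs from the SAP.** Threshold 0.05, no correction, three fixed-effect terms, 35 conditions, 1,485 trials, 6 subjects. The SAP gives no power or familywise error figure, so there is nothing of its own to reproduce.

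**Assumptions, not in the documents.** Delay and distance each enter as one numeric term, so there are three coefficients. Tests are two-sided and each holds its nominal 5% level. For the correlated case, the 35 conditions form a balanced 7 × 5 or 5 × 7 grid, with evenly spaced delays from 0 to 50 ms and evenly spaced distances from 500 to 4,000 in arbitrary units.

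**Chance of false support when all three true effects are zero**

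| Rule | Independent estimates | Uncentred predictors, assumed grid |
|---|---|---|
| Any one of three | 1 − 0.95³ = 0.143 | about 0.095 |
| Interaction alone | 0.05 | 0.05 |
| Joint 3-df test | 0.05 | 0.05 |
| All three | 0.05³ = 0.000125 | about 0.015 |

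Under any dependence, the any-one rule is bounded by 3 × 0.05 = 0.15. If one effect is real, the bound for the other two is 2 × 0.05 = 0.10. The all-three rule stays at or below 0.05 whenever at least one effect is zero, because that one test must itself be significant. The uncentred column comes from 1,000,000 multivariate normal draws of the three test statistics per grid. Starting the distances at 250 or 1,000 instead of 500 moves the any-one figure between about 0.091 and 0.098.

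**Can the verdict differ on the same output?** Yes. Take one coefficient with p = 0.01 and the other two estimates at zero, uncorrelated. Then z = 2.576 and z² = 6.635, and on 3 degrees of freedom the joint p is 0.084. That is support under any-one, but not under all-three or the joint test. If the significant coefficient is the interaction, it is also support under interaction-alone.

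**Is one rule plainly best?** No. Suppose three real effects with 80% power each.

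- Independent estimates: any-one 1 − 0.2³ = 0.992; all-three 0.8³ = 0.512; joint test 0.990 (noncentrality 3 × 2.8016² = 23.55, critical value 7.815).
- Uncentred predictors on the same grids, interaction opposite in sign to both main effects: about 0.90, 0.69 and 0.72.

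The gap between any-one and all-three falls from 0.992 − 0.512 = 0.48 to about 0.90 − 0.69 = 0.21. The cost of each rule therefore depends on coding and on effects that the SAP does not give.

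**What does the missing rule leave unchanged?** The three estimates, their standard errors and their p-values come from the same REML fit whichever rule is adopted. Only the summary sentence differs.

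**The case for a change.** The strongest case for a change is that the SAP labels a test as primary, calls its threshold pre-specified and states a hypothesis, and so invites a verdict. If that verdict may rest on whichever of three coefficients falls below 0.05, the error rate can approach 15%, and the stated reason for not correcting does not address this. One sentence would close the gap.

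A related point concerns coding. With an interaction in the model, the delay coefficient is the effect at distance zero. If b1 is the delay coefficient and b3 the interaction coefficient, centring distance replaces b1 by b1 + b3 × (mean distance), and the same happens for distance when delay is centred. The main-effect p-values therefore depend on a choice that the available text does not record. In a random-intercept model the joint test does not depend on it, but the SAP says only that subject is a random factor.

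Some of this stands. The rule is unstated, and the reason given for not correcting is not sufficient. The rest is weaker. In "Statistical significance was assessed with a pre-specified threshold of" 0.05, the advance commitment attaches to the threshold and is not a claim to control error across the three terms. Three questions, each answered by its own coefficient with non-correction disclosed, is common practice in exploratory work and agrees with the Introduction. The study-design hypothesis gives the interaction a clause of its own, so a reading in which that single 5% test decides is also fair.

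The results are written in the past tense, but that does not show that a rule was chosen after the data were seen. Part of the SAP was not available for review and may contain one.

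**Conclusion.** The gap is real and minor, and it does not call for a change. Correction would be needed only if any one of several coefficients could carry a confirmatory claim, and nothing in the SAP makes such a claim. If the tests are exploratory, if the interaction alone or a joint test decides, or if all three terms are required, leaving the p-values unadjusted is correct.

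The worst case is bounded at 15%, and is about 9 to 10% with uncentred predictors on the assumed grid. These figures assume three numeric terms, each tested at its nominal level. With 6 subjects the actual level could differ, which is a separate question.

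An analyst following the plan reports three estimates with unadjusted p-values and says that no correction was made, so readers can apply whichever rule they prefer. Choosing a rule for them would exchange one defensible position for another without altering a single estimate.

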## Outcomes

- **Primary Outcome:** The number of phosphenes elicited (num\_phosphenes) as a function of abs\_delay and dist\_ret.
